Clinical Study Protocol

Study Title: Impact of Providing Medical Records in a Patient-Centered, Community Pharmacy Based, HIV Care Model (HIV-MOI) of the Community Pharmacy-Based HIV Care Model study

ClinicalTrials.gov Identifier: NCT03437694

Sponsor: National Institute on Minority Health and Health Disparities

Sponsor Project Title: Texas Center for Minority Health, Education, Research and Outreach

FAIN Number: U54MD006882

IRB Number: 1436643/2018-094

Protocol Version/Date: Original Approval: 5/24/2019
Most Recent Approval: 10/17/2023

North Texas Regional Institutional Review Board (NTRIRB)

University of North Texas Health Science Center

PROTOCOL INFORMATION

Title of Research Activity: Medical record based versus non-medical record based community pharmacy provided medication therapy management

Name of Principal Investigator: [name], PharmD, BCIDP, BCPS (formerly known as [name])

Institution: UNTHSC

Sponsoring Agency / Company (if applicable): NIMHD

Sponsor's Protocol Number (if applicable): ClinicalTrials.gov Identifier: NCT03437694

Specific Aims –

- A. To investigate the change in control of diabetes and/or hypertension in adult African-Americans with HIV, who receive medication therapy management (MTM) from their community pharmacist when the pharmacist is provided the information from the participants' medical records (intervention) or not provided the information from the medical records (control, standard of care is no medical record information is provided). Control will primarily be determined using HgbA1c & plasma glucose from medical records (diabetes), and systolic blood pressure from medical records (hypertension) and these will be compared against nationally accepted standards for each condition. Control of HIV will be monitored (no change anticipated) via medical record provided HIV-RNA viral loads and CD4 counts.

Protocol version 9 October 2023

Medical record vs. Non-medical record

community pharmacy based MTM study

Page 1 of 31

B. Background and Significance

[figure not shown]

Figure 1: Adapted from Ribaudo 2016

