The **innovation** of medical record shared MTM is illustrated in the logic model (Figure 3): the sharing of a patient's medical information with the community pharmacist. *Figure 3 is a logic model only and not representative of the actual flow of the study, procedures or study requirements.* This proactive sharing of medical information prior to the pharmacist providing MTM is what is novel. The **impact** of this study is the likely demonstration that MTM improves the health in AA with HIV and discovers influences on MTM acceptability and uptake by patients, their community and providers. Knowledge gained can create a toolkit instructive on expanding MTM into additional communities with healthcare disparities and thereby multiply the impact of this limited measure.

C. Preliminary Studies

UNTHSC recently completed a 4-year demonstration/pilot project that was designed to develop a MTM program for persons with HIV. The demonstration project focus was to assess if MTM could be implemented in a community pharmacy. A secondary goal was to describe the impact on retention in care, viral load suppression and adherence to antiretrovirals. As that project's data analyses are ongoing, only partial results available.

Retention in care: Historical baseline data was that of the 1.2 million people in the US living with HIV, less than half were retained in care (Figure 5). MTM incorporated quarterly visits as a means to engage persons with HIV outside their clinic to see if this impacted retention in care. MTM visits (as compared to returning to medical clinic) permitted a novel approach to maintain engagement with patient. It also provided medical providers routine reports on the safety and effectiveness of the agreed upon medical plan. It worked. Of the 796 participants in the demonstration project, 98% (n=779) were retained in care. However, as a demonstration project, investigators were unable prove causality or assess for domains or levels of influence on why retention improved. This study is designed to demonstrate causality.

Virologic suppression: Preliminary analyses suggest improved outcomes in the 201 AA with HIV with data currently available. In AA with HIV (representing 48% of the CDC project enrolled participants), 85% achieved either virologic suppression (<20 copies/mL) or in those enrolled who already had virologic suppression, these participants CD4 count rose

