from below to above 200 cells/mcL. Both strongly suggest clinically significant improvements in control of HIV in AA.

Adherence to medications: these data are not currently available.

Although our CDC-funded demonstration project showed encouraging and promising results, it does not establish causal relationship between intervention and clinical outcomes. There was neither a control group nor random allocation of treatment. The primary critique of demonstration/pilot projects are the lack of scientific rigor to state cause:effect. Therefore, without the evidence this proposal will provide, the population that stands to see the most benefit from such an intervention, i.e., African-Americans, will not.

D. Investigator Experience

In combining post-graduate training and employment after my terminal degree, I have participated in the direct patient care management of a plethora of patient populations with infectious diseases (ID), including HIV. As a clinical pharmacist specialist and board certified in ID, I have a broad understanding of the multidisciplinary team nature of the delivery of HIV care and experience working collaboratively with other health professional disciplines at large academic medical centers, community hospitals, and hybrids of the two. The variety of patient populations and world-class patient care teams I have worked with and continue to work with at the University of Texas Southwestern Medical Center, has provided a solid practice foundation in the field of ID, inclusive of HIV. Correspondingly, prior to finishing my terminal degree, I worked as a pharmacy technician and intern at Walgreens where I personally delivered MTM services.

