Two hundred adult AA with HIV and either/both DM or HTN will be recruited using NTRIRB approved recruitment materials. Once consented, patient gender and comorbidity stratified randomization (i.e., separate randomization by men/women and by DM/HTN) will be used to randomize them into the intervention group or control. Randomization assignment will be controlled by the biostatistician. This will create eight groups: men with DM receiving intervention (1.a.), men with DM receiving control (2.a.), women with DM receiving intervention (1.b.), etc. (Figure 4). Patients with dual diagnosis of DM and HTN will be randomized into either the intervention or control group. Their data will be used in both DM and HTN analyses (after conducting a sensitivity analysis to determine that the dual diagnosis does not confound or bias the results). A random number generator (range 1 to 10,000) will be used for group assignment. UNTHSC biostatistician will be the only unblinded member of the research team to which number corresponds to the intervention or control groups when presenting data during investigator team safety reviews and data safety monitoring plan described.

The primary endpoint for this study will be the health indicators collected at the final follow-up visit comparing the corresponding intervention and control groups (e.g., intervention vs. control for men with diabetes). We computed the power and sample size based on the effect sizes estimated from our previous CDC-funded demonstration project where observations from 201 African American HIV patients at baseline whose viral loads were either detectable (>20 copies/mL) or their CD4 counts were <200 cells/mcL at baseline. Of these, 171 (85%) showed improvement (viral loads became undetectable or CD4 counts became >200 cell/mcL) at follow-up after receiving quarterly HIV-CMTM. Based on these results and even assuming a very conservative effect of 45% improvement for the control group receiving standard of care projects that a comparison between intervention and control will require 22 subjects per group. This enrollment volume enables attaining a power of at least 80% at the 0.05 level of significance for each of the comparisons. As some attrition is expected, we will recruit 25 patients per group for a total of 200 patients. We also note that the sample sizes are very likely larger as the subjects with a dual diagnosis of diabetes and hypertension will be included in the analyses, but are not included in the

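### F.1 claims at least 80% power for every sex-by-disease comparison, but its calculation uses only HIV inputs, so for diabetes and hypertension the figure is unsupported

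*Combined protocol and SAP*

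**What the plan says.** Section F.1 defines the endpoint in general terms, "The primary endpoint for this study will be the health indicators collected at the final follow-up visit", and compares the arms within sex-by-disease groups, with men who have diabetes as its example. The intervention rate comes from the earlier demonstration project: "Of these, 171 (85%) showed improvement (viral loads became undetectable or CD4 counts became >200 cell/mcL" at follow-up. The control rate is an assumption: "Based on these results and even assuming a very conservative effect of 45% improvement for the control group receiving standard of care". These two rates give 22 per group, raised to 25 for attrition, and eight groups make 200. The claim is then "This enrollment volume enables attaining a power of at least 80% at the 0.05 level of significance for each of the comparisons".

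F.1 adds that "the sample sizes are very likely larger as the subjects with a dual diagnosis of diabetes and hypertension will be included in the analyses", without a number. It also says that power was checked for continuous outcomes, but gives no endpoint, difference, SD or result.

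Other sections bear on these inputs:
- Section A makes control of diabetes and/or hypertension the aim and says of HIV: "Control of HIV will be monitored (no change anticipated) via medical record provided HIV-RNA viral loads and CD4 counts".
- Section E.2 lists HIV with diabetes and hypertension as the diseases used to judge effectiveness. It gives an A1c goal of 7% or below and, for hypertension, a 10 mmHg systolic reduction or attainment of goal. It names the t-test and chi-square test at 0.05.
- Section C says of the demonstration project: "There was neither a control group nor random allocation of treatment".

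**The concern.** A power statement belongs to an endpoint and an assumed effect. F.1 attaches one to every sex-by-disease comparison, yet its effect is a 40-point gap on an HIV composite, an outcome that Section A does not expect to change. Nothing shows that A1c or blood-pressure control would differ between arms by a comparable amount.

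The 40-point gap was not measured even for HIV. The demonstration project had no comparator, and in this trial the control arm also receives medication therapy management about every 90 days (Section E.1). A single-arm rate cannot show what sharing the records adds to that service. Nor does calling 45% conservative help: with the intervention rate fixed, a lower control rate makes the assumed effect larger and the required sample smaller.

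At stake is the reading of a null result. A reader who trusts F.1 could take a non-significant diabetes or hypertension comparison as an adequately powered negative. No section plans to report it that way, but the text permits it.

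**Working it through.** **Inputs.** From F.1: intervention rate 171/201 = 0.851, stated as 85%; control rate 45% (assumed there); level 0.05; power 80%; 22 per group needed and 25 recruited. From E.2: chi-square for categorical and t-test for continuous outcomes. Sidedness is not stated; two-sided is taken because it reproduces the plan's figure.

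**1. Reproduce the 22.** With p1 = 0.85, p0 = 0.45 and mean 0.65, the pooled formula without continuity correction is

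n = [1.960·√(2·0.65·0.35) + 0.842·√(0.85·0.15 + 0.45·0.55)]² / (0.40)²

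= (1.322 + 0.515)² / 0.16 = 21.1, so 22 per group. This matches.

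**2. Exact power for that contrast.** Summing the two binomial distributions over all tables that the uncorrected chi-square test rejects gives 81.7% at 22 per arm and 88.1% at 25.

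**3. Sensitivity to the assumed 45%.** The intervention rate stays at 85%; control rates other than 45% are assumptions.

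| Control rate | Power, 22 per arm | Power, 25 per arm |
|---|---|---|
| 35% | 95% | 98% |
| 45% | 82% | 88% |
| 50% | 72% | 79% |
| 55% | 60% | 67% |
| 65% | 34% | 39% |

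The highest control rate that keeps 80% power is 45.9% at 22 per arm and 49.5% at 25.

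**4. What the design detects on a binary outcome.** From an assumed 45% control rate, 80% power needs a true gap of 39.3 points at 22 per arm and 36.3 points at 25 (exact). At 22 per arm, power is 53% for a 30-point gap, 26% for 20 points and about 10% for 10 points.

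**5. What it detects on a mean.** Two-sample t-test power is P(|T| > t(0.975; 2n − 2)), with T noncentral t and noncentrality d·√(n/2). Setting it to 80% gives d = 0.865 SD at 22 per arm and 0.809 SD at 25.

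**6. Translation to systolic pressure.** E.2 states 10 mmHg as a reduction, not as a between-arm difference, and gives no SD. If 10 mmHg were the between-arm difference, 80% power would need an SD of at most 10/0.865 = 11.6 mmHg at 22 per arm, or 10/0.809 = 12.4 mmHg at 25. Power at 22 per arm would be 90%, 77%, 58%, 37% and 25% for assumed SDs of 10, 12, 15, 20 and 25 mmHg.

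**7. Search for another source.** The A1c goal and the systolic criterion in E.2 define control, but supply no expected rate, difference or SD. The continuous-outcome analyses in F.1 show no inputs. Dual-diagnosis participants would add numbers, but not an effect size.

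**The case against.** The best defence has five parts.

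- **HIV belongs to the plan.** E.2 names it among the effectiveness diseases and uses viral load as its t-test example, and F.1's endpoint is worded as health indicators in general. This stands: the HIV input is not foreign to the trial. But Section A anticipates no HIV change, so HIV's role needs reconciling, and the claim still extends to diabetes and hypertension comparisons.
- **The 85% may fit the intervention arm.** Section B says that pharmacists in the demonstration project had access to patients' medical information. This stands too. The missing comparator weakens the 45% and the 40-point gap, not the 85% as an HIV rate under record sharing.
- **The comparisons may be larger than 22 per arm.** Recruitment was planned at 25, and dual-diagnosis participants would add more. If sexes were pooled to 44 per arm (an assumption; F.1 describes separate comparisons), the detectable gap from 45% would fall to about 29 points and the control-rate limit would rise to about 59%. These figures soften the size of the problem, but the claim is made for each comparison at 22.
- **A narrow margin is ordinary.** Any sample sized to just reach 80% loses it soon after an assumption moves. That is fair, and the 45.9% limit is no fault in itself. It does show that 45% leaves almost no room at 22 per arm, which the word conservative would lead a reader to expect.
- **Nothing can be resized.** Section F.5 says that recruitment was complete by October 31, 2022, and Section E.5 ends visits on December 15, 2023. This confines the remedy to wording and reporting, where interpretation of a null result can still be corrected.

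**Conclusion.** The point holds in a limited form. For the HIV composite at 85% against 45%, F.1's sample size and power are correct. For diabetes and hypertension the 80% is unsupported, because none of its shown inputs concerns either disease.

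A reader might infer that the diabetes and hypertension comparisons are in fact underpowered. The documents do not show that: without a control rate, expected difference or SD, true power could lie on either side of 80%. A reader might also infer that 45% is too low because controls receive the same service without records. The documents give no control-arm rate, so its direction of error is unknown; what fails is only the unsupported description of it as conservative.

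The size is therefore conditional: about 39 points or 0.86 SD at 22 per arm, and about 36 points or 0.81 SD at 25. These figures assume a two-sided 0.05 level, the uncorrected chi-square test or the t-test and, for the gaps in points, a 45% control rate. The matter should be fixed, but it does not touch the validity of the randomised comparison.

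**What to change.** Keep the existing F.1 paragraph on record and add a dated clarification along these lines:

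*The 22 per group and the 80% power apply to the HIV viral-load/CD4 composite at 85% against an assumed 45%. They were not derived from diabetes or hypertension data. For those outcomes, 80% power (two-sided 0.05; chi-square without continuity correction, or t-test) holds only for a true gap of about 39 points from an assumed 45% control rate, or 0.86 SD, at 22 per arm, and about 36 points or 0.81 SD at 25 per arm. A 10 mmHg between-arm systolic difference would need an SD of about 11.6 mmHg or less at 22 per arm.*

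In addition:
- Justify the description of 45% as conservative, or drop it.
- State the endpoint, difference, SD and result of the continuous-outcome power analyses.
- Reconcile Section A with Section E.2 on whether HIV is an effectiveness outcome or is only monitored.
- Report each comparison's difference with a 95% confidence interval at the achieved numbers, including dual-diagnosis participants. Do not describe a null diabetes or hypertension result as an 80%-powered negative.

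The cost is wording and the intervals, with a less favourable stated power. Participants, tests and endpoints are unaffected.

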All study visits will take place over the phone or in-person. Participants who request in-person visits will meet with the research coordinator and/or study pharmacist in a room properly suited to accommodate the required distancing per the Center for Disease Control and Prevention's (CDC) recommended COVID-19 safety protocols for the immunocompromised populations. Social distancing will be observed, and the participants will be required to wear a facemask. After the in-person meetings for the consenting process and/or study visits are completed, hand sanitizers will be made available for disinfecting their hands.

5) *Estimated Period of Time to Complete the Study*

MTM sessions typically last up to 90 minutes for the first session then 30-45 minutes for each session thereafter. The UNTHSC assessments and survey are estimated to take 10 minutes or less per visit. Visits are encouraged to not exceed 90-day intervals. There are 8 planned quarterly visits, totaling 9 visits when including the consenting visit.

Due to funding limitations, the last day of study visits will occur on December 15, 2023. A formal memo to be sent via United States Postal Services (or similar university services) and text message verbiage will communicate the study termination to study participants. Participants who have been lost to follow-up, i.e. have not had a study visit in more than six months despite reminder communication, will not receive the physical memo or text message alert. Reimbursement for study visits will only occur for study visits that are

completed by the December 15th deadline.

F. Human Subjects - Describe the characteristics of the research population:

1) Sample Size:

Patient Identification, Recruitment (enrollment rate included in Power Calculation description below), Randomization, and Interim Analysis:

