Protocol version 9 October 2023

- Inability to self-administer medications (either due to mental or physical state)
- Hospice services currently being used or anticipated within the next year
- Systemic chemotherapy (topical chemotherapy allowed)
- Currently a prisoner or have received all healthcare to date as a prisoner

Early / Administrative withdrawal criteria:

Participants may be withdrawn from the study. Participants will be withdrawn from the study if they (i) voluntarily withdraw, (ii) demand to be switched to the other group after becoming aware of assignment, (iii) are lost-to-follow-up (moved), (iv) incarcerated, or (v) participant's care provider requests withdrawal. The PI will notify any participant terminated for any reason of the reason for termination from the study via phone call (voice mail left if no answer) using the following statement, "You are no longer able to participate in the study. The Walgreens study pharmacist has been notified. You may continue to use Walgreens for your pharmacy services if you choose to do so. Please contact [name] with questions about the study."

3) *Describe intended gender, age range, intended racial and ethnic distribution.*

The intended purpose of this study is to limit enrollment only to black/African-American adults (≥ 18) with a goal to enroll 50% women.

4) *Identify the source(s) from which you will obtain your study population.*

Study participants will be obtained from multiple sources. There is no requirement to be a Walgreens patient to participate in this study. Walgreens pharmacists are able to provide MTM to individuals who are not their patients.

5) *Describe plans for recruitment of subjects.* All materials (e.g., flyers, ads, emails, letters, postings, handouts, etc.) to be used for recruiting subjects must be submitted to the NTRIRB for review.

As of October 31, 2022, recruitment and enrollment of subjects are completed for the study. There are no current plans for further recruitment. Previous recruitment measures are provided below.

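### Visits stop on 15 December 2023, so late enrollees cannot complete two years; the attrition margin and the 80% power statement were not revised for this

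*Combined protocol and SAP*

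**What the plan says.** Section F.1 (Sample Size) places the primary endpoint at the final follow-up visit and compares matching intervention and control groups, for example men with diabetes in each arm. The sample size uses a response of 85% from the demonstration project ("Of these, 171 (85%) showed improvement") and a control rate obtained by "assuming a very conservative effect of 45% improvement for the control group". This gives 22 per group, of which F.1 says: "This enrollment volume enables attaining a power of at least 80% at the 0.05 level of significance for each of the comparisons". The margin follows: "As some attrition is expected, we will recruit 25 patients per group for a total of 200 patients". No attrition percentage is stated; 25 for 22 implies 3/25 = 12%.

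Section E.1 (Methods and Procedures) plans two years of data per participant, with visits about 90 days apart. Section E.5 (Estimated Period of Time to Complete the Study) counts eight quarterly visits after the consent visit, that is Visits 2 to 9, and then states: "Due to funding limitations, the last day of study visits will occur on December 15, 2023". Section F.5 (recruitment) states: "As of October 31, 2022, recruitment and enrollment of subjects are completed for the study". The version dated 9 October 2023 carries both the closing date and the power statement.

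**The concern.** The margin of 25 for 22 was set for ordinary attrition. The closing date is a second and separate reason for missing final-visit data, and F.1 makes no provision for it. Ordinary loss also continues: E.5 itself refers to participants with no visit for more than six months.

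Section E.2 names only a two-sample t-test and a chi-square test, and gives no rule for participants who cannot reach the final visit. If many were enrolled late, a null result would be read against 80% power that the final-visit comparison may not have. If they are instead analysed at whatever visit came last, the endpoint mixes different lengths of exposure and the plan does not say so.

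**Working it through.** **Inputs.** From F.1: response 0.85 and 0.45, significance level 0.05 (sidedness not stated; two-sided used), 22 needed and 25 recruited per group. From E.2: chi-square test. From E.1 and E.5: two years, Visits 2 to 9, last visit day 15 December 2023. From F.5: recruitment complete as of 31 October 2022. Assumptions: 25 per group were actually enrolled; accrual was uniform; it began no earlier than the original approval on 24 May 2019 (title page) and ran to 31 October 2022; enrolment is dated at Visit 2.

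**1. The plan's own figure.** With pooled proportion 0.65,

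n = [1.96·√(2·0.65·0.35) + 0.8416·√(0.85·0.15 + 0.45·0.55)]² / 0.40² = (1.322 + 0.515)² / 0.16 = 21.1, so 22.

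The stated 22 reproduces, and 22/0.88 = 25.

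**2. Power by number left per group.** Normal approximation: power = Φ[(0.40·√n − 1.322)/0.612]. The last column is the exact power of the uncorrected chi-square test.

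| n per group | Loss from 25 | Normal approx. | Exact chi-square |
|---|---|---|---|
| 25 | 0% | 86.6% | 88.1% |
| 22 | 12% | 81.7% | 81.7% |
| 21 | 16% | 79.8% | 81.9% |
| 20 | 20% | 77.7% | 79.5% |
| 19 | 24% | 75.4% | 78.4% |
| 18 | 28% | 73.0% | 75.4% |
| 16 | 36% | 67.5% | 70.6% |

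The margin is used up once more than 3 of 25 per group (3 × 8 = 24 of 200) lack final-visit data.

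**3. Cut-off dates.**
- 24 months before 15 December 2023 is 15 December 2021.
- Visit 2 to Visit 9 is seven intervals; 7 × 90 = 630 days, which gives 25 March 2022.
- A participant enrolled on 31 October 2022 would have at most 410 days.

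**4. Share enrolled too late, uniform accrual.** Share = (days from cut-off to 31 October 2022) / (days from accrual start to 31 October 2022).
- 24-month reading: 320/1256 = 25.5%; 18.6 of 25 left; power 74.6%.
- 630-day reading: 220/1256 = 17.5%; 20.6 left; power 79.0%.

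**5. Adding the planned 12% loss.**
- 24-month reading: 18.6 × 0.88 = 16.4; power 68.6%.
- 630-day reading: 20.6 × 0.88 = 18.1; power 73.4%.

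Exact power at 16 and 18 per group is 70.6% and 75.4%, so the two methods together span about 68–75%.

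**6. Sensitivity to the start date (assumed dates, normal approximation, closing date alone).**
- From 1 July 2020: 37.6% or 25.8% too late; power 66.3% or 74.3%.
- From 1 January 2021: 47.9% or 32.9% too late; power 57.9% or 69.7%.

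**7. Break-even.** For the closing date alone to cost no more than 12% on the 24-month reading, recruitment in the last 320 days must have run at no more than 12/25.5 = 0.47 of the average rate. On the 630-day reading the figure for the last 220 days is 12/17.5 = 0.69. In both cases nothing is then left for withdrawals.

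**The case against.** A reader might infer that the 12% margin has been exceeded and that 80% power is not delivered. The documents do not establish this, for five reasons.

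- **Accrual is unknown.** 31 October 2022 is a status date, not the date of the last enrolment. The protocol gives no first or last enrolment date, no accrual by date and no number enrolled. If few joined after mid-December 2021, the loss from the closing date is near zero and 22 per group still gives 81.7%.
- **90 days is not a minimum interval.** E.1 and E.5 treat it as a preferred upper limit, so someone enrolled after 25 March 2022 could still reach Visit 9 with closer visits.
- **The milder case is close to target.** On the 630-day reading with no other loss, 20 to 21 per group remain. Power is about 78–82% across the two methods, which is not a material shortfall.
- **The endpoint may survive truncation.** F.1 gives no month for the final follow-up visit. If it means the last visit attended, truncated participants keep an endpoint, though at less than two years.
- **There is an offset.** F.1 expects larger analysed samples because participants with both diabetes and hypertension enter both analyses.

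All five stand as reasons for conditional wording. None restores the statement in F.1. The dual-diagnosis number is not given, and F.1 makes its use follow a sensitivity analysis. The last-visit reading replaces a loss of numbers with an undefined mixture of follow-up times. It would also be wrong to infer an arithmetic slip, since both 22 and 25 reproduce.

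**Conclusion.** The conflict of dates holds without any accrual assumption: anyone enrolled after 15 December 2021 cannot complete two years, and F.1 neither counts such participants nor allows for them.

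The effect on power is conditional. With 25 enrolled per group, uniform accrual from 24 May 2019 to 31 October 2022, and 85% versus 45% taken at face value, the closing date alone leaves power of about 75–80%. The closing date plus the planned 12% loss leaves about 68–75%. A later start lowers these figures. Front-loaded accrual, closer visits or dual-diagnosis participants could reduce or remove the shortfall. The supportable conclusion is that the claim of at least 80% power for each comparison is no longer substantiated, not that it is shown to be false.

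**What to change.** 1. **F.1, power.** Replace the at-least-80% statement with the power computed from the actual number, for each comparison, able to reach the final time point by 15 December 2023. Enrolment is closed, so the sponsor already holds these counts. Report the number truncated by the closing date separately from ordinary withdrawals, and give the number of dual-diagnosis participants if they are relied on as an offset.
2. **F.1, endpoint.** State whether the final follow-up visit means 24 months or the last visit attended. If the latter, report follow-up time by arm.
3. **E.2, analysis.** Analyse all available medical-record values over time with a repeated-measures model that estimates the 24-month difference between arms, so that truncated participants contribute. State the missing-at-random assumption. It is plausible for truncation by calendar date and stronger for withdrawal. The model recovers some of the lost information, not all of it.

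The cost is a less favourable power figure and a little more analysis work. No further enrolment is proposed.
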